2.1 Change in planned analyses from the protocol

The protocol specifies that analyses are to be conducted by “patient group” which is formed by the types of cancer at study entry. That is, subjects with the same tumor type will be considered as in the same “patient group”. For efficacy analyses, with exception of the primary analysis of clinical benefit rate (i.e., summarized by ‘patient group’), other descriptive summaries in general will be produced overall for all BGJ-treated subjects. Separate summaries may be produced for those groups with at least 10 subjects. All subjects will be combined for any safety analyses.

In the event of a low response rate, DOR will only be listed, and not tabulated. Subjects who had no disease progression/death will be censored at last adequate tumor assessment on or before the discontinuation/completion of the study or data cut-off.

For determination of PFS events, due to tumor assessments post study treatment are not collected, deaths occurred more than 30 days post treatment without prior progressive disease/relapse of disease will not be considered as an event.

For vital signs, values will be descriptively summarized by nominal visit. Separate summaries of significant abnormalities will not be provided, but will be reflected in adverse events (AEs).

3 Subjects and treatments

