10.5 Secondary objectives

10.5.1 Key secondary objective(s)

The key secondary objective of this study is to assess Overall Response (OR) of Partial Response (PR) or greater based on local investigator assessment.

For patients with solid tumors the assessment criteria will be RECIST 1.1 and will include responses of CR and/or PR. For hematologic tumors other appropriate hematological response criteria will apply and are included in the appendices.

The overall response rate (PR or greater) and its 95% exact confidence interval will be provided for each patient group.

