6.2 Overall Response Rate (ORR)

Overall response is determined by investigator assessment for each tumor assessment in the study. For subjects with solid tumors (other than lymphoma) the assessment criteria will be RECIST 1.1 and will include responses of CR and/or PR; for lymphoma, Cheson criteria will be used; for hematologic tumors, other appropriate hematological response criteria will apply. The number and percentage of subjects for different categories of overall response (e.g., for solid tumors – CR, PR, SD, PD, Not Evaluable) will be provided for solid tumors (non-lymphoma), lymphoma (if applicable), and each hematological tumor type (if applicable). Ninety-five percent (95%) exact confidence intervals (CIs) will be provided for the response rate(s) (e.g., for solid tumors – CR and/or PR) as well. For cohorts with at least 10 subjects, overall responses will be summarized separately. Components of tumor assessments (e.g., for solid tumors – target lesion response, non-target lesion response, new lesion [yes/no]) will also be listed. In addition, Cancer Antigen-125 (CA-125) (if applicable) in the assessment of ovarian cancer response, Prostate-specific Antigen (PSA) (if applicable) in the assessment of prostate cancer will be listed.

The above analyses will be performed for the FAS.

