10.1.2 Trial Logistics

Each trial will enroll all available subjects in all cohorts for 2 years unless a cohort cap is reached, or a cohort is stopped early, or the trial is stopped early by Novartis. Each trial will enroll no more than 30 evaluable subjects in each cohort. Interim monitoring will be conducted starting after the first 30 subjects are enrolled overall (across all cohorts), and continuing each 13 weeks thereafter till study enrollment closure. After that, one CBR analysis will be done after database lock. At each interim data review, response information for the various cohorts will be evaluated to determine the current $\Pr(\theta_g > 0 | \text{data})$ within each cohort, with sufficiently high/low values used to stop the cohort for success/futility. A minimum of 10 subjects will be required in a cohort before it may discontinue enrollment for futility, and a minimum of 15 subjects are required before discontinuing a cohort for efficacy. If a cohort stops enrolling early, the remaining cohorts will continue until the end of 2 years or until the other cohorts reach their own early stopping criteria. The final analysis will occur after the database lock for the primary CSR.

Each trial will enroll subjects in all listed cohorts. In addition, should other cohorts be identified throughout the trial, the following mechanism will be used. If another cohort is identified, it will not be placed into the statistical analysis unless 3 subjects enroll within the cohort (thus, the trial may enroll multiple additional cohorts, but a cohort will only be added to the list if at least 3 subjects enroll from that cohort). Thus, it is possible (but not viewed as likely) that multiple additional cohorts may be added to the trial if the trial has sufficient enrollment in multiple additional cohorts. In addition to sufficient enrollment, the sponsor must have a reasonable estimate of the control clinical benefit rate.

Subjects within any cohort which does not reach the minimum enrollment will be excluded from the interim and final analyses. As the study continues, early interim data reviews may be based on fewer cohorts than later interim data reviews, as the interim data reviews will include whatever cohorts have satisfied the criteria at the time of the data review.

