10.4.1 Assumptions

Accrual – Two scenarios for the assumed two-year expected accrual are investigated: 1) 10 subjects per group and 2) 5 subjects per group. Note that these are averages, the actual number of available subjects is simulated as a Poisson distribution with the specified mean.

Also note that the group cap of 30 applies, and thus if the number of available subjects in a group exceeds 30, only the first 30 available subjects in that group will be enrolled in the study.

Dropouts – We assume no dropouts for the purpose of this simulation.

Control Rates – Table 1 shows the assumed control clinical benefit rates for each group.

Table 1 – Controlled CBR values used in the simulations	
Tumor Type	Assumed Control Rate (R_g)
Lung LSCL	0.45
Bladder	0.47
Breast	0.50
Colorectal	0.38
GIST	0.50
HNSCC	0.45
Ovarian	0.47
Sarcoma	0.40

We consider four possible scenarios, or possible “truths” in the simulation. These consisted of a null scenario (where the treatment has no effect for any group), an alternative scenario (where the treatment is effective in all groups), a scenario where the treatment was effective in two of the groups, and a scenario where the treatment was effective in half of the groups.

Treatment Rates - The treatment rates for each scenario are shown in the table below. Values identical to the control are shown in normal text, while values greater than the assumed control rate are shown in bold.

	Null	Alternative	Two	Half
Lung LSCL	0.45	0.71	0.45	0.45
Bladder	0.47	0.73	0.47	0.47
Breast	0.50	0.75	0.50	0.50
Colorectal	0.38	0.65	0.38	0.38
GIST	0.50	0.75	0.50	0.75
HNSCC	0.45	0.71	0.45	0.71
Ovarian	0.47	0.73	0.73	0.73
Sarcoma	0.40	0.67	0.67	0.67

Simulation Details – For each scenario we simulated 1000 trials. For each interim within each trial, we ran 50,000 MCMC iterations after a 1,000 MCMC iteration burnin.

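### The SAP limits a cohort's own ORR to cohorts of 10 or more, against the protocol and without a reason, so a smaller cohort can be declared a success on CBR with no tabulated ORR or interval beside it

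*SAP*

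**What the plan says.** Protocol 10.5.1 sets no size limit for the key secondary endpoint: "The overall response rate (PR or greater) and its 95% exact confidence interval will be provided for each patient group".

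SAP 2.1, which lists changes from the protocol, keeps CBR by tumour type but says of the remaining efficacy analyses that "other descriptive summaries in general will be produced overall for all BGJ-treated subjects". It then adds: "Separate summaries may be produced for those groups with at least 10 subjects".

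SAP 6.2 sets the default grouping for ORR. The response categories "will be provided for solid tumors (non-lymphoma), lymphoma (if applicable), and each hematological tumor type (if applicable"), with exact 95% intervals for the response rates. For single tumour types it says: "For cohorts with at least 10 subjects, overall responses will be summarized separately".

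Neither section says why the limit is 10. The two also differ in force: separate summaries *may* be produced under 2.1 and *will* be produced under 6.2.

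**The concern.** The study looks for a signal tumour type by tumour type. Its primary decision is made separately for each cohort, and the Amendment 3 rationale cites observed responses in the six tumour types it re-opened. A pooled ORR is the weighted mean Σ(n_g × p_g) / Σn_g over cohorts, so its value depends on the enrolment mix. It does not show which tumour types responded. The pool also includes tumour types closed to new patients by Amendment 3.

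ORR matters most next to CBR. CBR counts stable disease of at least 16 weeks as well as response, so a high CBR can arise from either. SAP 6.1 also makes confirmed responders who stop before week 16 for reasons other than progression non-evaluable for CBR. For those patients, ORR is the rate in which the response would be counted. If a small cohort is declared a success on CBR, the reader needs its response count and interval in the same place.

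**Working it through.** **1. Can a cohort below 10 receive a CBR decision?**

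- An added cohort enters the CBR analysis from 3 patients (SAP 10.1.2; SAP 10.1 says 4 or more).
- Early success needs 15 evaluated patients (SAP 10.3.2), so a small cohort cannot stop early for success.
- The final rule, posterior probability above 0.90, has no minimum size (SAP 10.3.3). Nor does the promising category, 0.80 to 0.90 (SAP 6.1).

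So it can, but only at the final analysis.

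**2. How likely is a cohort to fall below 10?**

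The documents give no figure for this, so there is none to reproduce. The only accrual model is in Protocol Appendix R and SAP 10.4.1: two-year expected accrual of "1) 10 subjects per group and 2) 5 subjects per group", "simulated as a Poisson distribution with the specified mean". Futility stopping needs 10 patients and early success 15, so early stopping cannot leave a cohort below 10. The cap ("Each trial will enroll no more than 30 evaluable subjects in each cohort") has no effect either.

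P(N < 10) = Σ e^(−m) m^k / k!, for k = 0 to 9.

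The first two rows below are the plan's scenarios. The others assume that the SAP's planned total of 70 to 90 (SAP 2) is spread evenly, an assumption the documents do not make.

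| Accrual | Mean m | P(N < 10) | Expected cohorts below 10 |
|---|---|---|---|
| Scenario 1, eight cohorts | 10 | 0.458 | 8 × 0.458 = 3.7 |
| Scenario 2, eight cohorts | 5 | 0.968 | 8 × 0.968 = 7.7 |
| 70 over eight | 70/8 = 8.75 | 0.620 | 5.0 |
| 90 over eight | 90/8 = 11.25 | 0.314 | 2.5 |
| 70 over the six re-opened | 70/6 = 11.67 | 0.273 | 1.6 |
| 80 over the six re-opened | 80/6 = 13.33 | 0.145 | 0.9 |
| 90 over the six re-opened | 90/6 = 15 | 0.070 | 0.4 |

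Protocol 5.1 gives 70 to 120 patients. At 120 the probability is 0.070 over eight cohorts (m = 15) and 0.005 over six (m = 20).

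Conditioning on entry to the CBR model changes little. With at least 3 patients, the scenario values are 0.456 and 0.964; with at least 4, they are 0.452 and 0.957.

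**3. Do the scenarios match planned enrolment?**

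Eight cohorts at mean 10 give 80 patients, inside 70 to 90. Eight at mean 5 give 40, well below it.

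**4. Does precision change at 10?**

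Exact (Clopper-Pearson) 95% intervals:

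- 3/9: 7.5% to 70.1%; 3/10: 6.7% to 65.2%.
- 0/9: upper limit 33.6%; 0/10: upper limit 30.8%.
- 0/5: upper limit 52.2%.

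Intervals are wide on both sides of the limit, and nothing distinct happens at 10.

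**The case against.** The SAP names this change openly in the section meant for such changes. ORR carries no hypothesis test and no power requirement (SAP 2 and 9), and a size floor for descriptive rates is a common reporting choice. An interval that reaches 52% after 0/5 says little. All of this is true, and it keeps the point to one of reporting. It does not explain why a protocol commitment on the key secondary endpoint was narrowed, or why 10 was chosen.

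A reader might infer from the Poisson scenarios that about half or more of this trial's cohorts will lack an ORR. The documents do not support that as a forecast. Appendix R and SAP 10 describe a framework for all modules, using eight example cohorts. These include breast, colorectal, GIST and sarcoma but not glioblastoma or cholangiocarcinoma. The mean-5 scenario does not fit the planned total. The Amendment 3 rationale says each re-opened cohort stays open until 10 patients are evaluable for futility. If that is met, all six pass the limit. However, the rule is not carried into Protocol section 10, Appendix R or the SAP, and SAP 10.1.2 lets enrolment end at two years or by sponsor decision. Meeting it would also leave other cohorts in the CBR model uncovered.

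A reader might also infer that a CBR success made of stable disease could not be told from one driven by responses. That goes too far. SAP 2 puts all collected data in listings, and SAP 6.2 lists the components of each tumour assessment. What is missing is the tabulated cohort rate and its interval.

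Nor are cohort summaries purely optional. Section 6.2, which governs ORR, makes them firm at 10 or more; the two sections need reconciling.

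**Conclusion.** The point holds as an unexplained narrowing of a protocol commitment. A cohort below 10 can be declared a success or promising on CBR at the final analysis with no tabulated ORR or interval of its own.

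The number of cohorts affected cannot be fixed from the documents. P(N < 10) is 46% and 97% under the generic scenarios, the second implying too few patients for the plan. With 70 to 90 patients spread evenly, it is 62% down to 31% over eight cohorts and 27% down to 7% over the six re-opened types. The six-cohort range is favourable, because some of the total belongs to tumour types now closed. It is none of the six if the Amendment 3 target is reached. The reporting gap in the rule exists whichever of these applies.

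**What to change.** In SAP 2.1 and 6.2:

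- Report responders/N, ORR and exact 95% interval beside CBR for every cohort in the CBR model, and for all six re-opened tumour types whatever their size.
- Label the pooled solid-tumour ORR as descriptive.
- Reconcile *may* in 2.1 with *will* in 6.2.
- Keep the 10-patient limit for the Kaplan-Meier summaries of PFS and OS only.

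This restores the rule in Protocol 10.5.1. It needs no new data and adds a few rows to an existing table. The downside is wide intervals in small cohorts; showing them helps guard against over-reading a small cohort's rate.

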7.1.4.2 Efficacy follow-up

Not applicable.

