10.5.2 Other secondary efficacy objectives

The secondary efficacy objectives of the study:

- To assess progression free survival (PFS) based on local investigator assessment per RECIST 1.1 or other appropriate hematological response criteria
- To assess overall survival
- To assess duration of response (DOR) based on local investigator assessment per RECIST 1.1 or other appropriate hematological response criteria

The secondary efficacy variable progression free survival (PFS) is defined as the time from the date of first dose to the date of first documented disease progression or relapse or death due to any cause.

PFS will be summarized and graphed using the Kaplan-Meier product-limit method for each patient group. Patients who drop-out without progression will be censored at the time of last adequate assessment. The estimates of the 25th, median, 75th percentiles of the PFS and their 95% confidence intervals will be provided, if applicable.

Overall survival (OS) is defined as the time from the date of first dose to the date of death due to any cause. If a patient is not known to have died, survival time will be censored at the date of the last contact.

OS will be summarized and graphed using the product-limit method as above.

The duration of response (PR or greater) applies only to patients whose best response was PR or greater. For patients with solid tumors the assessment criteria will be RECIST 1.1 and will include responses of CR and/or PR. For hematologic tumors other appropriate hematological response criteria will apply and are included in the appendices. The duration of response is defined as the time from the first documented response to the date first documented disease progression or relapse or death due to any cause. The duration of response will be summarized descriptively for each patient group.

If the study primary efficacy endpoint is not met, Novartis may decide not to conduct some of the above secondary efficacy analyses but instead provide those endpoints in listings only.

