6.3 Progression Free Survival (PFS)

PFS is defined as the time from the date of first dose of BGJ398 to the date of the first documented disease progression/relapse or death due to any cause within 30 days of the last dose, and is calculated as $PFS = (\text{date of progression/relapse or death} - \text{date of first study treatment} + 1)$. Disease progression noted as the reason for discontinuation of treatment will be considered as a progression, thus will be considered as an event for PFS.

Subjects who discontinue or complete study treatment without disease progression will be censored at last adequate tumor assessment on or before the discontinuation/completion of the study. For subjects who are still on study treatment at the time of data cut-off date for the primary analyses, PFS will be censored at the last adequate tumor assessment before the data cut-off date for the analysis of PFS on the primary CSR. For subjects who have no tumor assessment post baseline, PFS will be censored at Day 1. The final CSR (i.e., addendum to the primary CSR) will utilize additional PFS data obtained from these subjects after the primary CSR cut-off date.

PFS will be summarized and graphed using the Kaplan-Meier product-limit method¹. The estimated median survival time, the corresponding 95% CIs², and 25th and 75th percentiles will be provided. In addition, survival rate estimates at 1, 2, 3, 4, 5, 6, and 12 months with 95% CIs will also be provided. For cohorts with at least 10 subjects, separate PFS analyses will be conducted for each cohort.

The above analyses will be performed for the FAS.

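### The SAP narrows the protocol's PFS definition to deaths within 30 days of the last dose, and its unqualified Day 1 censoring rule contradicts the SAP's own event definition

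*SAP*

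**What the plan says.** Protocol 10.5.2 (and Table 3-1) measures PFS from first dose to the "date of first documented disease progression or relapse or death due to any cause", with no time limit on the death. It also censors drop-outs without progression at their last adequate assessment. Protocol 7.1.4.2 plans no efficacy follow-up after treatment.

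SAP 2.1 announces a change: "deaths occurred more than 30 days post treatment without prior progressive disease/relapse of disease will not be considered as an event". Its reason is "due to tumor assessments post study treatment are not collected".

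SAP 6.3 carries this into the definition, where the death component becomes "death due to any cause within 30 days of the last dose". It also states "Disease progression noted as the reason for discontinuation of treatment will be considered as a progression", so those patients already have an event. In the censoring paragraph it adds: "For subjects who have no tumor assessment post baseline, PFS will be censored at Day 1". The Day 1 sentence is neither in the protocol nor among the changes listed in SAP 2.1.

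**The concern.** There are two separate problems.

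**The window is tied to the wrong date.** If the difficulty is that nobody scans after treatment, what matters is how long before death the patient was last known to be progression-free. The SAP measures from the last dose instead. Scans are 8 weeks apart up to week 16 and 16 weeks apart afterwards, so a death can fall well before the next scan was due and still not count.

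**The Day 1 rule has no condition.** A patient who dies within 30 days of the last dose without a post-baseline scan is an event under the first sentence of SAP 6.3 and a Day 1 censoring under the later one. Two programmers could code this patient differently.

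Patients who stop without progression and die soon afterwards are likely to have a poor prognosis. Censoring them treats their later risk as equal to that of patients still under observation. SAP 6.3 plans separate PFS curves for cohorts of 10 or more, where a few such patients can move the curve.

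**Working it through.** The documents give no PFS assumption, event count or power, so there is no planned figure to reproduce.

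**1. The Day 1 conflict.** First dose Day 1, last dose Day 20, no scan, death Day 40. The gap is 40 − 20 = 20 days, so the death is an event, with PFS = 40 − 1 + 1 = 40 days by the SAP formula. Under the Day 1 sentence the same patient is censored at Day 1.

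**2. The 30-day window against the scan schedule.** A clean scan falls on Cycle 5 Day 1 (Day 113); the next is due 16 weeks later, on Day 225. Treatment stops for toxicity with the last dose on Day 120, and death follows on Day 155.
- Death is 155 − 120 = 35 days after the last dose, so it is not an event.
- It is 155 − 113 = 42 days after a clean scan and 70 days before the next was due.
- No end-of-treatment scan was required. Table 7-1 footnote 3 asks for one only if the previous scan is at least 8 weeks old. The visit falls within 14 days of stopping (Protocol 7.1.3.1), by about Day 134, when the scan is 21 days old.

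The dosing schedule uses up part of the window. With the last dose on Day 21 and the next intended on Day 29, a 14-day interruption reaches Day 43, already 22 days after the last dose.

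**3. How many patients might be concerned.** Phase I stop reasons (Protocol 1.2.1.2.1) serve as a proxy. Stops for neither progression nor death were 28 + 15 + 1 + 1 = 45 of 186 (24%). Without the 15 consent withdrawals they were 30 of 186 (16%).

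**4. A 20-patient example.** Five patients stop on Day 25 unscanned. The other 15 progress: 6 on Day 56, 5 on Day 112 and 4 on Day 224.
- *The five die on Day 70.* Protocol: 14/20 = 70% after Day 56, 9/20 = 45% after Day 70, 4/20 = 20% at Day 180; median 70 days. SAP (five censored at Day 1): 9/15 = 60%, then 4/15 = 27% at Day 180; median 112 days.
- *The five die on Day 400.* Protocol: 9/20 = 45% at Day 180. SAP: still 27%. Both medians are 112 days.

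The SAP figure is higher in the first case and lower in the second.

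**5. Simulation against the protocol definition.** 100,000 patients per scenario. Assumptions not taken from the documents: exponential times, stopping independent of progression, all deaths known, progression dated at the next scheduled scan. The rows below use a 24% stop share and no end-of-treatment scans. Entries are 6-month PFS; the last column applies the Day 1 sentence literally.

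| Median progression (months) | Mean survival after stop (months) | All deaths | SAP, deaths ≤30 days count | SAP, Day 1 rule literal |
|---|---|---|---|---|
| 2.5 | 2 | 0.266 | 0.286 (+2.0 points) | 0.301 (+3.5) |
| 2.5 | 16 | 0.391 | 0.326 (−6.5) | 0.329 (−6.2) |
| 4 | 2 | 0.431 | 0.462 (+3.1) | 0.478 (+4.7) |
| 4 | 16 | 0.533 | 0.505 (−2.8) | 0.507 (−2.6) |

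With an end-of-treatment scan in everyone, the last two columns coincide. Without such scans, 5 to 12% of patients had no post-baseline scan.

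**6. Simulation against a scan-based window.** The comparator counts deaths within 16 weeks of the last adequate scan, or of first dose if there is none. Inputs: 16% or 24% stops, median progression 3 or 5 months, median survival after stopping 2, 4 or 6 months, end-of-treatment scan in none or all. The SAP rule gave higher 6-month PFS in all 24 scenarios, by 1.2 to 3.9 points. That sign is expected, because the window rule mainly adds events. Over the same survival range, SAP minus all-deaths ran from about −3 to +3 points.

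**The case against.** The 30-day rule is disclosed, with a reason, in the section meant for departures from the protocol. Protocol 10.5.2 itself censors drop-outs without progression at the last adequate assessment. PFS carries no hypothesis test (SAP 2) and no power consideration (SAP 9). The clinical benefit rate is untouched, and known deaths remain in overall survival (SAP 6.4) and the death listing (SAP 7.2). Table 7-1 footnote 3 requires a scan at end of treatment for anyone stopping before the first scheduled one, so an unscanned early stopper has missed a mandated assessment. All of this stands and limits the weight of the point.

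It could also be said that a censoring sentence naturally applies only to patients without an event. But the neighbouring sentences state their conditions (no progression, or still on treatment), and this one states none.

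A reader might infer more than the documents support:
- *That every death after 30 days is dropped.* Only deaths without prior progression or relapse are, and progression given as the reason for stopping already counts as an event.
- *That these deaths are all known.* Protocol 7.1.4.3 limits survival follow-up to six tumour types, excludes withdrawn consent, and allows follow-up not to be done if the primary endpoint is missed.
- *That PFS will be judged against historical data.* Historical rates are specified for clinical benefit only (Protocol 10.4.3, SAP 6.1).

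**Conclusion.** The point holds as a narrowing of the protocol definition with a poorly matched window, plus an internal contradiction over unscanned patients who die within 30 days. The contradiction needs correcting whatever its effect on the estimate, because it can give a patient the wrong event status.

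The size is modest and rests on assumptions. It is about 1 to 4 points of 6-month PFS relative to a 16-week scan-based window, given 16 to 24% non-progression stops, median progression of 3 to 5 months and median survival after stopping of 2 to 6 months. It is tempting to conclude that the SAP rule makes PFS read high in general, but that is not established. Relative to the protocol's own definition the difference runs from about −3 to +3 points over that range and reaches −6.5 with longer survival. Counting a late death as the event treats the patient as progression-free through months without scans. The 16-week comparator is in neither document, and its choice as a main rule is debatable.

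**What to change.** - In SAP 6.3, state that Day 1 censoring applies only to patients with no PFS event, and list the rule in SAP 2.1.
- Report PFS under the protocol definition, counting all known deaths.
- As a further sensitivity analysis, tie the death window to the last adequate assessment instead of the last dose.
- Give the number of deaths excluded by the 30-day rule and the number of patients censored at Day 1, overall and for each cohort with its own PFS curve.

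The cost is a few sentences and two extra Kaplan-Meier runs on dates already collected. PFS may look less favourable, and late deaths will be known only in patients under survival follow-up, which the report should state.
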